3.5.7.1.3 Adverse Events of Special Interest

Adverse events of special interest are a subset of AEs that include potentially immune-mediated medical conditions (autoimmune or auto-inflammatory diseases) that may have the theoretical potential for association with novel vaccines. All participants enrolled in the study will be monitored for new onset of AESI from Day 1 through Month 13. The occurrence of any of these AEs will be treated as an SAE, meeting the criterion of a "medically important event."

The list of AESI is presented in Appendix 2.

A diagnosis of an AESI will be reported to the Sponsor in an expedited manner, similar to an SAE (Section 3.5.7.3). The AESI diagnosis, as well as any medications taken to treat the condition, will be recorded in the participant's eCRF.

3.5.7.1.4 Pregnancy

To ensure participant safety, each pregnancy in a participant after study vaccination must be reported to the Sponsor or designee within 72 hours of the site learning of its occurrence. If the participant agrees to submit this information, the pregnancy must be followed to determine the outcome, including spontaneous or voluntary termination, details of the birth, and the presence or absence of any birth defects, congenital abnormalities, or maternal and/or newborn complications. This follow-up should occur even if intended duration of the Long-Term Follow-up Phase for the study has ended.

Pregnancy report forms will be distributed to the study site to be used for this purpose.

The investigator must immediately (within 24 hours of awareness) report to the Sponsor any case of pregnancy resulting in an abnormal outcome (miscarriage or newborn with congenital abnormality and/or stillbirth) according to the procedures described for SAEs.

3.5.7.2 Eliciting and Documenting Adverse Events

The investigator is responsible for ensuring that all AEs, SAEs and AESI are recorded in the eCRF and reported to the Sponsor. Unsolicited AEs will be assessed during the Vaccination Phase from the time of the first dose administration at Day 1 through Day 57 (±7 days). Serious AEs, MAAEs, and AESI will be assessed from Day 1 through Month 13 (EOS Visit), as specified in the Schedule of Events (Table 5). Any AEs occurring before receipt of the vaccine will be analyzed separately from TEAEs.

At every clinic visit or telephone contact, participants will be asked a standard question to elicit any medically-related changes in their well-being according to the scripts provided. Participants will also be asked if they have been hospitalized, had any accidents, used any new medications, or changed concomitant medication regimens (both prescription and over-the-counter medications).

In addition to participant observations, data from clinical laboratory test results, physical examination findings, or other documents relevant to participant safety classified as an AE will be documented on the AE page of the eCRF.

3.5.7.3 Reporting Adverse Events

All unsolicited AEs reported or observed during the study will be recorded on the AE page of the eCRF. Information to be collected includes dose group assignment and dose, type of event, time of onset, investigator-specified assessment of severity and relationship to vaccine, time of resolution of the event, seriousness, as well as any required treatment or evaluations, and outcome. The unsolicited AEs resulting from concurrent illnesses, reactions to concurrent illnesses, reactions to concurrent medications, or progression of disease states must also be reported. All AEs will be followed until they are resolved or stable or judged by the investigator to be not clinically significant (NCS). The Medical Dictionary for Regulatory Activities (MedDRA) will be used to code all unsolicited AEs.

Any medical condition that is present at the time that the participant is screened but does not deteriorate should not be reported as an unsolicited AE. However, if it deteriorates at any time during the study, it should be recorded as an unsolicited AE.

Any AE or AESI considered serious by the investigator or that meets SAE criteria (Section 3.5.7.1.2) must be reported to the Sponsor immediately (within 24 hours of becoming aware of the SAE or AESI). The investigator will assess whether there is a reasonable possibility that the vaccine caused the SAE or AESI. The Sponsor will be responsible for notifying the relevant regulatory authorities of any SAE or AESI as outlined in the 21 US Code of Federal Regulations (CFR) Parts 312 and 320. The investigator is responsible for notifying the institutional review board (IRB) directly.

If the eCRF is unavailable at the time of the SAE or AESI, the following contact information is to be used for SAE reporting:

SAE Mailbox: PPD

SAE Hotline (USA and Canada): PPD

SAE Fax line (USA and Canada): PPD

3.5.7.4 **Assessment of Severity**

The severity (or intensity) of an AE refers to the extent to which it affects the participant's daily activities. When applicable, the Toxicity Grading Scale for Healthy Adult and Adolescent Volunteers Enrolled in Preventative Vaccine Clinical Trials (DHHS 2007) will be used to categorize local and systemic reactogenicity events (solicited AEs), clinical laboratory test results, and vital sign measurements observed during this study. Specific criteria for clinical and laboratory abnormalities are presented in Appendix 3 (Table 6 and Table 7, respectively) and will be graded if outside of the reference range for the laboratory utilized.

The determination of severity for all unsolicited AEs not listed in Toxicity Grading Scale should be made by the investigator based upon medical judgment and the definitions of severity as follows:

Mild: These events do not interfere with the participant's daily activities.

- Moderate: These events cause some interference with the participant's daily activities but do not require or require limited medical intervention.
- Severe: These events prevent the participant's daily activity and require intensive therapeutic intervention.

Changes in the severity of an AE should be documented to allow an assessment of the duration of the event at each level of intensity to be performed. An AE characterized as intermittent requires documentation of onset and duration of each episode.

In the case where an AE meets the definition of a serious AE (SAE), refer to Section 3.5.7.1.2.

3.5.7.5 Assessment of Causality

The investigator's assessment of an AE's relationship to vaccine is part of the documentation process but is not a factor in determining what is or is not reported in the study.

The investigator will assess causality (i.e., whether there is a reasonable possibility that the vaccine caused the event) for all AEs, AESIs, and SAEs. The relationship will be characterized using the following classification:

- Not related: There is not a reasonable possibility a relationship to the investigational product. Participant did not receive the investigational product OR temporal sequence of the AE onset relative to administration of the investigational product is not reasonable OR the AE is more likely explained by another cause than the investigational product.
- Related: There is a reasonable possibility of a relationship to the investigational product. There is evidence of exposure to the investigational product. The temporal sequence of the AE onset relative to the administration of the investigational product is reasonable. The AE is more likely explained by the investigational product than by another cause.

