3.3.2 Participant Withdrawal From Study Vaccine

Every reasonable attempt will be made to follow up with participants for safety throughout the entire study period, even if further vaccination is withheld or the participant misses one or more visits.

Unless consent is withdrawn, a participant who discontinues from receiving the second dose of study vaccine will remain in the study and complete all safety and immunogenicity procedures required through 1 month after the last vaccination received per the Schedule of Events (i.e., up to Visit 5/Day 29 for subjects receiving only the first dose of vaccine).

Subjects will then enter the 12-month Long-Term Follow-up Phase per the Schedule of Events (Table 5).

The investigator, in consultation with the Sponsor's medical monitor, **may** withhold a participant **from further vaccination** if the participant experiences any of the following:

- Becomes pregnant
- Develops, during the course of the study, symptoms or conditions listed in the exclusion criteria
- Experiences an AE (other than reactogenicity) after vaccination that is considered by the investigator to be possibly or probably related to vaccine and is of Grade 3 (severe) or greater severity (Appendix 3)
- Experiences an AE or SAE that, in the judgment of the investigator, requires study vaccine withdrawal due to its nature, severity, or required treatment, regardless of the causal relationship to vaccine
- Experiences a CS change in clinical laboratory test results, vital sign measurements, or general condition that, in the judgment of the investigator, requires vaccine withdrawal
- Experiences anaphylaxis clearly attributed to study vaccine
- Experiences generalized urticaria related to the study vaccine

The reason(s) for withdrawing further vaccination will be recorded.

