3.5.7.1.1 Definitions

An AE is defined as any untoward medical occurrence associated with the use of a drug in humans, whether or not considered drug related. Participants will be instructed to record any AEs (solicited or unsolicited) in the diary card.

A treatment-emergent AE (TEAE) is defined as any event not present before exposure to vaccine or any event already present that worsens in intensity or frequency after exposure.

A suspected adverse reaction is any AE for which there is a reasonable possibility that the vaccine caused the AE. For the purposes of investigational new drug safety reporting, "reasonable possibility" means that there is evidence to suggest a causal relationship between the vaccine and the AE. A suspected adverse reaction implies a lesser degree of certainty about causality than adverse reaction, which means any AE caused by a vaccine. Adverse reactions are a subset of all suspected adverse reactions for which there are reasons to conclude that the drug caused the event.

An unsolicited AE is any AE reported by the participant that is either (1) not specified as a solicited AE in the protocol or (2) specified as a solicited AE in the protocol, but its onset occurs outside of the protocol-defined post-vaccination period for reporting solicited AEs (i.e., for the 7 days after each vaccination; Section 3.5.6 for additional information on solicited safety measures).

An AE or suspected adverse reaction is considered "unexpected" if it is not listed in the IB or is not listed at the specificity or severity that has been observed with the vaccine being tested or, if an IB is not required or available, it is not consistent with the risk information described in the general investigational plan or elsewhere in the current application. For example, under this definition, hepatic necrosis would be unexpected (by virtue of greater severity) if the IB referred only to elevated hepatic enzymes or hepatitis. Similarly, cerebral thromboembolism and cerebral vasculitis would be unexpected (by virtue of greater specificity) if the IB listed only cerebral vascular accidents. "Unexpected," as used in this definition, also refers to AEs or suspected adverse reactions that are mentioned in the IB as occurring with a class of drugs or as anticipated from the pharmacological properties of the drug but are not specifically mentioned as occurring with the particular drug under investigation.

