7.6.2.3 TEAEs by System Organ Class and Preferred Term

The following summary tables of TEAEs will be provided by MedDRA SOC and PT using frequency counts and percentages (i.e., number and percentage of participants with an event) for all participants, for all flavivirus seropositive participants and for all flavivirus seronegative participants. When summarizing the number and percentage of participants with an event, participants with multiple occurrences of the same AE or a continuing AE will be counted once. Only the maximum severity level will be presented and an AE with missing severity will be counted as Grade 3/severe in the severity summaries. Only the strongest relationship level will be presented and an AE with missing relationship will be counted as related in the relationship summaries.

- All unsolicited TEAEs
- All unsolicited treatment-related TEAEs
- All unsolicited TEAEs through 7 days after any vaccination
- All unsolicited treatment-related TEAEs through 7 days after any vaccination
- All unsolicited TEAEs of Grade 3 or higher through 7 days after any vaccination
- All unsolicited treatment-related TEAEs of Grade 3 or higher through 7 days after any vaccination
- All unsolicited TEAEs of Grade 2 or higher through 7 days after any vaccination
- All unsolicited treatment-related TEAEs of Grade 2 or higher through 7 days after any vaccination
- All unsolicited TEAEs of Grade 3 or higher through 28 days after any vaccination
- All unsolicited treatment-related TEAEs of Grade 3 or higher through 28 days after any vaccination
- All unsolicited TEAEs of Grade 2 or higher through 28 days after any vaccination
- All unsolicited treatment-related TEAEs of Grade 2 or higher through 28 days after any vaccination

- All unsolicited TEAEs within 60 minutes after any vaccination
- All unsolicited treatment-related TEAEs within 60 minutes after any vaccination
- All unsolicited serious TEAEs after any vaccination
- All unsolicited serious treatment-related TEAEs after any vaccination
- All unsolicited TEAEs of special interest after any vaccination
- All unsolicited treatment-related TEAEs of special interest after any vaccination

7.6.3 **Clinical Laboratory Evaluations**

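### Protocol 3.5.7.5 asks whether vaccine causation is a reasonable possibility but sorts the answer by which cause is more likely, so sites can rate the same event differently

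*Protocol*

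**What the plan says.** Protocol 3.5.7.5 sets the task: "The investigator will assess causality (i.e., whether there is a reasonable possibility that the vaccine caused the event) for all AEs, AESIs, and SAEs". It then defines two levels. Each opens with the presence or absence of a reasonable possibility, and each adds further criteria.

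- *Related* also requires exposure and plausible timing, and ends with "The AE is more likely explained by the investigational product than by another cause".
- *Not related* lists three alternatives joined by OR: no exposure, implausible timing, or "the AE is more likely explained by another cause than the investigational product".

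The same underlying standard appears elsewhere in the protocol without a comparison of causes. Section 3.5.7.1.1 states: "A suspected adverse reaction is any AE for which there is a reasonable possibility that the vaccine caused the AE". For IND safety reporting it adds that a reasonable possibility "means that there is evidence to suggest a causal relationship between the vaccine and the AE", and then: "A suspected adverse reaction implies a lesser degree of certainty about causality than adverse reaction". Section 3.5.7.3 puts the reasonable-possibility question to the investigator again for SAEs and AESIs.

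Section 3.3.2 refers to an event "considered by the investigator to be possibly or probably related to vaccine", which uses levels that the two-level scale does not contain. Section 3.4.2.3 uses the word *related* for SAEs and AESIs, which is on the scale.

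The SAP takes the recorded rating as it stands. Section 7.6.2.1 repeats each overview category for treatment-related events, 7.6.2.2 includes a preferred-term table by relationship, and 7.6.2.3 has a series of tables starting with "All unsolicited treatment-related TEAEs". A missing relationship is counted as related; a recorded *Not related* is left unchanged. SAP Section 8 does not mention the definition.

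**The concern.** A reasonable possibility and a more-likely-than-the-alternative judgement are different thresholds, and the second is stricter. By placing both inside the same two categories, 3.5.7.5 leaves the investigator without one rule for events that could plausibly come from the vaccine but have another plausible explanation. In healthy adults followed for 28 days after each injection, a headache or a mild laboratory change with an intercurrent illness in the background is the kind of event this describes.

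In a first-in-human dose-ranging study the related-event tables are a natural first place to look for a dose pattern. If sites, or investigators within a site, resolve the text differently, some variation in those tables will reflect how the definition was read.

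**Working it through.** **Step 1: set the criteria against the possible judgements.** Take an event with exposure and plausible timing, so that only the causal judgement varies.

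| Investigator's judgement | Reasonable possibility? | Last condition of *Related* | Likelier-alternative ground of *Not related* | Category |
|---|---|---|---|---|
| A. No reasonable possibility | No | Not met | Usually met | *Not related* |
| B. Reasonable possibility, other cause likelier | Yes | Not met | Met | Parts of both |
| C. Reasonable possibility, causes equally likely | Yes | Not met | Not met | Neither in full |
| D. Reasonable possibility, vaccine likelier | Yes | Met | Not met | *Related* |

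A and D are clear. B and C are not, and neither 3.5.7.1.1, 3.5.7.3 nor the SAP says which criterion prevails.

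**Step 2: direction.** If the question asked decides, the related events are B + C + D. If the last condition of *Related* is enforced literally, they are D alone. The difference is B + C, which cannot be negative. The literal count is therefore equal to or lower than the count under the reasonable-possibility standard. The SAP default for missing relationship does not offset this, because B and C events carry a recorded rating.

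**Step 3: where the rating is used.** SAP 7.6.2.3 lists 18 tables in nine pairs: all TEAEs; through 7 days; Grade 3 or higher through 7 days; Grade 2 or higher through 7 days; Grade 3 or higher through 28 days; Grade 2 or higher through 28 days; within 60 minutes; serious; special interest. One of each pair is restricted to treatment-related events, so 9 of 18 depend on the rating. So do the related half of the 7.6.2.1 overview and the by-relationship table in 7.6.2.2. The classification of suspected adverse reactions depends on it to the extent that it uses the investigator's rating.

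**Step 4: what one participant is worth.** Group sizes are from Protocol Table 1.

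- Dose group: 1/24 = 4.2 percentage points.
- Seronegative vaccinees in a dose group: 1/20 = 5 points.
- Seropositive vaccinees in a dose group: 1/4 = 25 points. The 7.6.2.3 tables are also produced by serostatus.

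**Step 5: illustration of scale.** The documents give no figure for the share of events in B or C. The only AE-counting figure is in Protocol 3.6.4, and it reproduces from 1 − (1 − p)^24:

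- p = 0.10: 1 − 0.90^24 = 0.920 (stated 92%)
- p = 0.05: 1 − 0.95^24 = 0.708 (stated 70.8%)

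Now assume that p is the incidence of events with a reasonable possibility of vaccine causation, and that a share m of them is moved out of *Related* by the literal reading. The chance of at least one related case among 24 is 1 − (1 − p(1 − m))^24, and the expected count is 24p(1 − m).

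| m (assumed) | p = 0.10: chance | expected | p = 0.05: chance | expected |
|---|---|---|---|---|
| 0 | 92.0% | 2.4 | 70.8% | 1.2 |
| 10% | 89.6% | 2.16 | 66.9% | 1.08 |
| 25% | 84.6% | 1.8 | 60.0% | 0.9 |
| 50% | 70.8% | 1.2 | 45.5% | 0.6 |
| 75% | 45.5% | 0.6 | 26.1% | 0.3 |

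The width of this range shows that the size rests on m, which the documents do not supply. The table is not an estimate of what happened.

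**The case against.** The strongest reply is that the text still works in practice and that little depends on it. Several parts of that reply stand.

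- The question put to the investigator is reasonable possibility, and so is the opening of *Related*. An investigator who answers that question and stops loses no events. A reader might infer that the treatment-related tables will undercount; the documents show only that they could.
- The explanation of reasonable possibility in 3.5.7.1.1 is expressly for IND safety reporting, so it is not a general definition that 3.5.7.5 breaches. The inconsistency does not need it, because it is already present within 3.5.7.5.
- A reader might also infer that safety reporting or the primary endpoints are compromised. They are not. Section 3.5.7.5 says that the rating does not determine what is reported, 3.5.7.3 sends SAEs and AESIs to the sponsor within 24 hours whatever the rating, and the endpoints in 3.6.1 count events regardless of relationship.
- Each related table in SAP 7.6.2.3 has an all-causality partner for the same window and grade, so no event disappears from view.
- Pause rules 1, 2, 5 and 6 carry their own attribution wording, and rules 3 and 4 carry none.
- Site ratings are made blinded, so the stricter clause is not directed at one arm.

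These points limit the reach of the problem but do not remove it. The pairing of tables does not make the related column consistent, and nothing in either document tells two investigators how to treat a B or C event alike.

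**Conclusion.** The point holds as an internal inconsistency in a stated rule. Section 3.5.7.5 asks one question and classifies partly by another. Events with a likelier alternative cause meet parts of both categories, and events with equally likely causes fully meet neither.

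Read literally, the related count is equal to or lower than under the reasonable-possibility standard. The amount is not determinable, because it depends on how many events fall in that zone and on how each investigator read the text. The firm figures are 4.2 percentage points of a dose group per reclassified participant, and 9 of 18 SOC/PT tables exposed.

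The reach is confined to the treatment-related summaries in SAP 7.6.2.1 to 7.6.2.3, the suspected-adverse-reaction classification so far as it uses this rating, and protocol text that refers to related events. Only 3.3.2 uses terms outside the scale. Section 3.4.2.3 does not, but what its word *related* means inherits the ambiguity.

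**What to change.** - **Recorded rating and tables.** In 3.5.7.5, remove the comparative clause from both categories, so that the two levels answer the question asked: reasonable possibility, or none. Add an eCRF completion note saying so.
- **Events already rated.** State in the SAP and the study report which wording applied, by cohort. Cohorts are dosed in sequence, so a change part-way would otherwise put different dose groups under different definitions.
- **Terms elsewhere.** Reconcile the off-scale terms in 3.3.2 with the two-level scale. Separately, the sponsor should state how *related* in 3.4.2.3 is to be read, since that section concerns further vaccination. This review does not choose the threshold there, and the change to the recorded rating should not settle it by default.

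The cost is protocol wording, a completion note and a sentence or two in the SAP and report. Related rates may come out somewhat higher, and a mid-study change needs consistent handling across cohorts. Design, sample size and primary endpoints are unaffected.

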3.5.7.6 Follow-up of Adverse Events

All AEs, SAEs, and AESI must be reported in detail on the appropriate page of the eCRF and followed until the event is resolved or stable or judged by the investigator to be NCS.

